#### 1. EXECUTIVE SUMMARY.

## 1.1 Study Title

Clinical Study to Evaluate the Efficacy of Surface Electrical Stimulation for Urge Urinary Incontinence in Women.

# 1.2 Objectives

The primary objective is to demonstrate the safety and efficacy of the ELITONE-UUI device for urge urinary incontinence.

# 1.3 Design and Outcomes

This is a case series with two treatment groups. Pre- and post-study outcome measures evaluate the change in incontinence episodes (i.e. leaks), leaks, bathroom visits, and quality of life.

## 1.4 Interventions and Duration

Participants will self-administer electrical stimulation using the ELITONE-UUI device, 20-25 minutes per session, 4-5x per week, for 6 weeks. Participants will be randomly assigned to one of two groups, each group receiving a different device configuration wherein the stimulation frequency (e.g. 10Hz, 50Hz) differs between the groups. The ELTIONE-UUI device is identical to Elidah's ELITONE device, except for the digitally controlled stimulation parameters.

## 1.5 Sample Size and Population

The population includes women ages 21-80 with mild-moderate urge urinary incontinence or mild-moderate mixed urinary incontinence with predominant urge symptoms. The study intends to have 20 women complete the study in each group.

#### 2. OBJECTIVES AND HYPOTHESES

# 2.1 Primary Objective

The primary objective of this study is to demonstrate the safety and efficacy ELITONE-UUI device as a conservative treatment for urge urinary incontinence.

## 2.2 Primary Endpoint

Treatment efficacy is assessed by comparing the average number of urinary incontinence episodes per day at the end of treatment to the corresponding pre-treatment number.

Safety is determined by review of Adverse Events as defined in 7.3, and determination of no serious adverse event during the study.

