## 5.2 Number of Subjects

20 subjects per treatment group (40 total). Appreciating that some subjects who are initially enrolled will fail to complete treatment and return the study materials, it is likely that 50-55 subjects will be enrolled. See 9.1 for discussion of the sample size calculation.

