#### 7.3 Adverse Events and Serious Adverse Events

Adverse events are the primary means for assessing device/treatment safety. Adverse events may be identified through direct communication with the subjects and through analysis of study materials.

For all adverse events, sufficient information will be pursued and/or obtained so as to permit (1) an adequate determination of the outcome of the events (i.e., whether the effect should be classified as a serious adverse effect) and (2) an assessment of the causal relationship between the adverse event and the device/treatment.

Adverse events determined to be associated with the device/treatment will be followed until they are resolved or stabilized. The CTCAE definitions and scoring of Adverse Events will be used.

An **adverse event (AE)** is generally defined as any unfavorable and unintended symptom or finding which either occurs during the study, having been absent at baseline, or, if present at baseline, appears to worsen during the study. Adverse events are recorded regardless of their relationship to the study intervention.

A **serious adverse event (SAE)** is generally defined as any adverse event that results in death, is life threatening, requires inpatient hospitalization or prolongation of existing hospitalization, results in persistent or significant disability/incapacity, or is a congenital anomaly: Grades 3-5.

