## 9.4 Interim Analyses and Stopping Rules

Due to the short duration of the study (6 weeks) and likely rapid enrollment (1 month), there are no plans for an interim analysis.

In the event of a serious adverse event related to the device/treatment the study will be halted until the safety issue can be addressed (see 7). Due to the small enrollment size, a pre-specified number of adverse events will not be used to trigger an early end to the study.

\_

<sup>2 Richardson et al, "Pelvic floor electrical stimulation: A comparison of daily and every-other-day therapy for genuine urge incontinence", Adult Urology, 48(1):110-118, 1996.

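### The primary safety endpoint rests on zero serious adverse events with no statement on relatedness and no planned analysis, and about 40 women are too few for a zero count to demonstrate safety

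*Combined protocol and SAP*

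**What the plan says.** All references are to the combined protocol and SAP.

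- **Objective.** Section 2.1 sets out "to demonstrate the safety and efficacy ELITONE-UUI device as a conservative treatment for urge urinary incontinence". Section 1.2 says much the same.
- **Endpoint.** Section 2.2 reads: "Safety is determined by review of Adverse Events as defined in 7.3, and determination of no serious adverse event during the study". It has two limbs, a review of adverse events and the absence of serious ones. The first has no criterion, and the second does not mention relatedness.
- **Recording and definition.** Section 7.3 says "Adverse events are recorded regardless of their relationship to the study intervention". Its definition of a serious event includes one that "requires inpatient hospitalization or prolongation of existing hospitalization", and ends by tying seriousness to Grades 3-5.
- **Causality.** Section 7.3 also asks, for every adverse event, for enough information to permit "an assessment of the causal relationship between the adverse event and the device/treatment".
- **Halting.** Section 9.4 does use relatedness: "In the event of a serious adverse event related to the device/treatment the study will be halted until the safety issue can be addressed".
- **Analysis.** Section 5.3 names adverse events as the primary safety outcome and refers to 9.5 for the analysis. Section 10.6 says that 9.5 holds the approach used to judge study success. Section 9.5 covers efficacy, secondary outcomes and usability only. It gives no safety rate, denominator, analysis set or interval.
- **Size.** Section 5.2 plans 20 women per group, 40 in all, and expects to enroll 50-55 to reach that number.

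**The concern.** Safety is half of the primary objective, and sections 6.7 and 9.6 say that the study is meant to support FDA clearance. Its only explicit criterion can mislead in two directions.

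First, the endpoint and the halting rule use different event definitions. An admission that everyone agrees has nothing to do with the device would not halt the study under 9.4, yet on the literal wording of 2.2 it would break the safety criterion. Whether such an event counts would then be settled after it had happened.

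Second, a zero count meets the serious event limb, and the objective invites the reader to take that as demonstrated safety. In a sample of this size, a zero count is compatible with serious event rates that few would accept for a device described as low risk.

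The denominator is also open. The efficacy analysis in 9.5 uses adherent women, and section 8 lists a recurring adverse event among the reasons to end a woman's treatment. If the same set were used for safety, women withdrawn for harm could drop out of the count.

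**Working it through.** **1. The plan's own figures.** The documents give no safety sample size, tolerable rate or confidence limit. The group sizes in 9.1 (31, 16 and 12) come from efficacy responder rates: 48% v 13%, 62% v 13% and 71% v 15%. Section 9.1 does not state alpha or power. With two-sided 5% and 90% power assumed, and unpooled variance,

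n = [p1(1-p1) + p2(1-p2)] × (1.960 + 1.282)² / (p1-p2)²

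gives 32, 16 and 12 after rounding up, which is within one woman of each stated figure. These sizes carry no information about the precision of a safety rate.

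**2. What a zero count excludes.** For 0 events in n women the exact (Clopper-Pearson) upper limit is 1 - 0.025^(1/n) for a two-sided 95% interval, and 1 - 0.05^(1/n) for a one-sided 95% limit.

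| n | Source | Two-sided | One-sided |
|---|---|---|---|
| 20 | one configuration, 5.2 | 16.8% | 13.9% |
| 40 | both configurations, 5.2 | 8.8% | 7.2% |
| 50 | lower enrollment figure, 5.2 | 7.1% | 5.8% |
| 55 | upper enrollment figure, 5.2 | 6.5% | 5.3% |

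The last two rows are best cases. Under 4.3 a woman becomes a subject at consent, and under 5.4 she can be disqualified on her baseline log before any device is sent. Not all 50-55 need be treated.

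**3. How often a real risk stays hidden.** The chance of no event in 40 women is (1-p)^40. If the true serious event risk were 5%, this is 0.95^40 = 12.9%. If it were 2%, it is 0.98^40 = 44.6%.

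**4. How often an unrelated event would break the criterion (illustration only).** Forty women for 6 weeks give 40 × 6/52 = 4.6 person-years. The documents state no background rate, so the rates below are assumptions. The chance of at least one event is 1 - exp(-rate × 4.6).

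| Assumed unrelated serious events per 100 person-years | Chance of at least one |
|---|---|
| 1 | 4.5% |
| 3 | 13% |
| 10 | 37% |

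**5. Is the serious event count defined?** Section 7.3 lists the usual seriousness outcomes and then adds Grades 3-5. On the scale in 7.4, grade 3 is a severe event, for example one that leaves a woman temporarily unable to do an everyday activity and in continuing need of medical attention. Such an event need not involve admission, threat to life or lasting disability. The two sections can therefore classify the same event differently. Section 7.3 also says that CTCAE scoring applies, while 7.4 sets out a 0-5 scale of its own.

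**The case against.** The strongest reply is that this is a descriptive case series. Sections 2.3, 9.1 and 9.5 all say that it is not hypothesis driven, and 9.5 sets no serious event threshold for success. Three stronger readings are tempting, and the documents do not support them.

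- *A reader might infer that any serious event makes the device fail.* No section says so. The documents state no consequence for the device, and the inference rests only on a missing qualifier.
- *A reader might infer that the endpoint is a test of zero serious events alone.* The adverse event review is a second limb, so a zero count is necessary but not literally sufficient. Section 7.1 also rests the low-risk assessment on other grounds: a software-only difference from a cleared device, the non-significant risk designation and third-party electrical testing.
- *A reader might infer that the safety result depends mainly on background admissions.* At the assumed rates above, 63% to 95.5% of such trials would see no unrelated serious event. Section 4.2 excludes several groups in poorer health, so a low rate is plausible.

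It can also be said that an all-cause count is a defensible conservative choice. A related-only count would rest on judgments made while study staff know the assignment (5.7, 9.3) and by a board that includes the sponsor's Clinical Director (10.5). That stands, and it is why the fix keeps both counts.

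The rest does not remove the problem. A second limb without a criterion supplies no decision rule. The supporting evidence in 7.1 puts no interval around this study's rate. A descriptive design is a reason to report an estimate with its uncertainty, not to keep a zero-event determination under an objective to demonstrate safety.

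**Conclusion.** The point holds as a defect in definition and analysis. The only explicit criterion of the primary safety endpoint does not say whether unrelated events count, differs from the halting rule in this respect, and has no analysis behind it in 9.5, where 5.3 and 10.6 send the reader.

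A zero count would leave serious event rates of up to 8.8% unexcluded for 40 women and up to 16.8% for each configuration of 20 (exact two-sided 95%). With one-sided limits these are 7.2% and 13.9%, and the conclusion is the same. Even if 55 women were treated, the two-sided limit would be 6.5%. None of these supports the word demonstrate.

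These limits depend only on n and the confidence level. The 4.5% to 37% chance of an unrelated event rests on assumed rates and shows only that the ambiguity could matter. The planned data collection is adequate, because causality is already to be assessed for every event.

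**What to change.** 1. **Sections 2.2 and 9.5.** In 2.2, replace the zero-event determination with the number and proportion of women with at least one serious adverse event. Give all-cause and device-related counts side by side, with relation unknown counted as related. Use as denominator all women who applied the device at least once. Give exact 95% confidence intervals overall and by configuration. Enter the same analysis in 9.5.
2. **Precision.** State there that 0 of 40 excludes only rates above 8.8%, and 0 of 20 only rates above 16.8% (two-sided 95%).
3. **Sections 1.2 and 2.1.** For safety, change the verb from demonstrate to describe.
4. **Sections 7.3 and 7.4.** Reconcile the Grades 3-5 tag with the grade 3 definition, and say which grading scale applies, so that the serious event count has one meaning. The choice is for the sponsor.

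The cost is wording in these sections, settled before any outcome data are reviewed. No new data are needed. The sponsor gives up the claim of demonstrated safety for a more modest statement.

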## 2.3 Hypothesis

This case series is not a hypothesis driven study. The expectation is that both treatment groups will realize a clinically meaningful reduction (≥50%) in urinary incontinence episodes per day

relative to a pre-treatment baseline. Secondary measures may also show clinically meaningful changes. Differences between the groups may inform selection of a device configuration to move toward product commercialization.

## 2.4 Secondary Objectives

The secondary objectives are to characterize the device's efficacy at improving continence based on other meaningful clinical endpoints. This data may be useful to support future product marketing claims including support for over-the-counter use. Further, certain information may inform opportunities for future product improvements.

# 2.5 Secondary Endpoints:

Endpoints that support the secondary objectives are listed below. Further description is provided in 5.3 and 9.5.

- Incontinence Quality of Life score (I-QoL)
- Pads per Day
- Urge Incontinence Episodes without a Leak
- Urge Incontinence Episodes with a Leak
- Bathroom Visits per Day
- Nighttime Bathroom Visits
- Usability Data (e.g. Ease of Use, Satisfaction, Preferred Intensity Settings)
- Treatment Compliance

#### 3. BACKGROUND AND STUDY RATIONALE

## 3.1 Background on Condition, Disease, or Other Primary Study Focus

Urinary incontinence (UI) is a widely prevalent condition affecting approximately 1 in 3 women over the age of 30, and 1 in 2 women over the age of 50.1,2,3 Although a very private concern, it has far-reaching physical, psychological, social, and economic implications. For example: UI has been found to reduce health-related quality of life measures, with a strong correlation with depression,4 UI is the number one reason for entry into nursing homes, and the annual cost to Medicare has been estimated at \$10 billion, and at \$20 billion for the entirety of the US healthcare system. Often women do not want the medication that is available for Urge Urinary Incontinence (UUI) due to potential interference with other medications. There are implantable and percutaneous electrical stimulation devices, which can provide relief although can be expensive or require weekly office visits.

Electrical muscle stimulation (EMS) of the pelvic floor muscles and surrounding structures has proven effective in treating UUI and multiple "e-stim" devices have received FDA clearance to treat UUI (e.g. Intone, Kegel8, Yarlap). However, these devices deliver the stimulation via an intravaginal probe. Women often find this method uncomfortable. Further, these intravaginal devices necessitate a private location and dedicated treatment time (often at a treatment center), which challenges the likelihood of adoption.

To complicate matters, 4 out of 5 sufferers do not speak with their primary care physician until symptoms have intensified and persisted for numerous years (6.5 years on average), and others do not consult a specialist (i.e. urologist) because they fear the recommendation of surgery. This

leads to two thirds of affected women suffering quietly without treatment while conditions worsen. Thus, the need exists for a non-invasive means of treating UUI that has a higher rate of patient adoption and compliance than current solutions.

# 3.2 Study Rationale

Surface electrodes have been used for EMS and transcutaneous electrical nerve stimulation (TENS) applications since the 1970's. They have an established history of safe and efficacious across a range of anatomic application sites, and the FDA considers electrodes to be low risk devices: "Electrodes are a Non-significant risk device, no IDE needed" (Non-implantable Electrical Incontinence Device).9

There is a long history of use of intravaginal EMS for treatment of SUI and UUI, and it is predicated on the assumption that proximity of the electrodes to the pelvic floor and bladder is of primary importance. This is largely accurate. However, appreciating that subjects who seek help most often ultimately fail treatment due to adoption and compliance issues, it is equally important to consider whether the psychological or physiological barriers associated with intravaginal devices offset any benefit from the treatment's intimate electrode placement.

Clinical reports have suggested that a pattern of surface electrodes placed in the suprapubic and ischial tuberosity regions are as effective as intravaginal electrodes at treating SUI and UUI. 10,11,12,13 In these studies, treatment was administered by a clinician who placed four separate electrodes on the defined tissue region and delivered prescribed pulse waves during regular training sessions. Unfortunately, the need to deliver this treatment in a clinical environment makes it burdensome to the patient and the health system.

Building on these findings, Elidah developed a wearable, use-at-home SUI specific muscle stimulation device called ELITONE. Elidah has conducted clinical trials of ELITONE (WIRB 20162650, WIRB 20180640) and observed clinically meaningful improvements in SUI symptoms without serious adverse events. For example, the subjects reported an average reduction in leaks of 72%, and 75% of subjects had a clinically significant (≥50%) reduction in leaks. That device received FDA clearance as an SUI treatment in 2019.

Elidah now seeks to evaluate an alternate device configurations of the ELITONE device in which the output has been changed to a frequency understood to more directly affect UUI symptoms. Throughout this protocol the UUI device configurations are referred to as ELITONE-UUI.

#### 4. SELECTION AND ENROLLMENT OF PARTICIPANTS

#### 4.1 Inclusion Criteria

All subjects must meet the inclusion criteria below to participate in this study. Any waiver of these inclusion criteria (or the subsequent exclusion criteria) must be approved by the Clinical Director on a case-by-case basis prior to enrolling the subject, and documented in the subject's Case Report Form (TR-1155-FORM-10).

- Predominant urge urinary incontinence as determined by responses to a series of three standard questions from the King's Health Questionnaire; specifically:
  - An affirmative response to "Is it very difficult to control when you have a strong urge to urinate?",

- An affirmative or negative response to "Do you lose urine with physical activities such as coughing, sneezing, running?",
- And, if an affirmative response to the second question, an affirmative response to "Are more of your incontinence episodes due to a strong urge to urinate than to abdominal pressure such as sneezing?"
- Mild-moderate incontinence symptoms as determined by self-reported typical number of accidents of 1 or more per 24 hours. Symptom severity is later verified with data from the Daily Log (See 5.4)

Age: 21-80yGender: Female

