#### 4.2 Exclusion Criteria.

Subjects will be excluded from enrollment if they meet any of the following criteria:

- Less than 1 incontinence accident (leak) per day\*
- Severe incontinence as determined by self-reported >5 accidents per day
- Currently pregnant, may be pregnant, attempting to become pregnant, or delivery within previous 6 weeks
- Vaginal or pelvic surgery within previous 6 months
- Severe Obesity as defined by BMI >= 35
- Change in incontinence medication type or dosing within the last 3 months.
- History or symptoms of urinary retention, extra-urethral incontinence, overflow incontinence
- Pelvic pain/painful bladder syndrome
- Active urinary tract infection (UTI) or history of recurrent UTIs (more than three in a year), or recurrent vaginitis (bacterial/fungal)
- Tissues protruding outside the vagina at rest
- Presence of incontinence-associated dermatitis or other perineal skin disorders or lesions,
- Complete denervation of the pelvic floor
- Conductive inter-uterine devise (IUD/Coil) or metal implants in the abdominal or pelvic area, including the hip and lumbar spine,
- Chronic coughing
- Previous use of Interstim device or Botox for UI
- Implanted cardiac device, untreated cardiac arrhythmia or suffer from other heart problems.
- Cancer, epilepsy or cognitive dysfunction
- Underlying neurologic/neuromuscular disorder
- Impaired decision making, suicidal thoughts, or drug/alcohol dependence
- Lacks capacity to consent for themselves.

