# 5.7 Blinding

Subjects will be blinded to the treatment group. Study staff will not be blinded to the treatment group. This is done to enable staff to respond to questions regarding the timing (i.e. on/off cycles) of the stimulation, which is treatment group specific. See 9.3 for addition discussion of blinding.

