## 9.2 Randomization

Subjects are assigned to a treatment group at the time the device is shipped to the subject. Assignments are made alternating between Group 1 and 2 until enrollment is complete.

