## 10.5 Data and Safety Monitoring Plan

Elidah will identify a Clinical Director who will be responsible for managing the study and ensuring that the rights and well-being of human subjects are protected, that the reported data are accurate and complete and verifiable from source documents, and that the conduct of the trial is in compliance with the approved protocol, with good clinical practice, and with applicable regulatory requirements. Specific responsibilities of the Clinical Director include:

- Verify that equipment and staff are adequate to safely and properly conduct the study
- Verify that subjects:
  - Meet eligibility requirements
  - o Provided informed consent prior to enrollment
  - Are adequately informed about the device use, study requirements and risks of participation
  - Receive all necessary study materials
  - Return all the required data collection forms and specimens
- Verify that, with respect to the device:
  - That shelf-life and storage conditions meet requirements (as applicable)
  - o Sufficient supplies (i.e. electrodes, controllers) are sufficient to complete the study
  - o That the device is provided only to eligible subjects
  - o That the receipt, use, and return of the device is controlled and complies with applicable regulation.
- Verify that source documents and data analyses are accurate and complete
- Verify that adverse events are appropriately reported
- Verify that protocol deviations are appropriately reported

In addition, a Data Safety and Monitoring Board will be established which will review study compliance and adverse events. The Data Safety and Monitoring Board will comprise, at a minimum, the Clinical Director, an individual responsible for technological aspects of the device and an individual with medical training relevant to the used of the device.

EMS and TENS devices (including the ELITONE device) are sold over the counter and used in an at-home environment. Given the high degree of similarity between those devices and the ELITONE-UUI device, the described level of monitoring is considered appropriate for the low level of risk (see 7).

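### Section 4.1 lets one role waive any eligibility criterion without an independent check or an analysis rule, in conflict with 5.4, 10.5 and 11.2

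*Combined protocol and SAP*

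**What the plan says.** Section 4.1 first requires every participant to satisfy the criteria, then opens an exception: "Any waiver of these inclusion criteria (or the subsequent exclusion criteria) must be approved by the Clinical Director on a case-by-case basis". Approval must come before enrolment and be noted in the Case Report Form. Those are the only conditions. No criterion is named as non-waivable, no grounds or maximum number are given, and neither 4.1 nor 9.5 says how a woman admitted by waiver is to be analysed.

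The exception extends to the whole of 4.2. That list includes "Implanted cardiac device, untreated cardiac arrhythmia or suffer from other heart problems", together with pregnancy, epilepsy, metal or conductive implants, lack of capacity to consent, and the limits of fewer than 1 and more than 5 accidents per day.

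On the role itself, 10.5 says: "Elidah will identify a Clinical Director who will be responsible for managing the study". The same section has the Clinical Director verify eligibility and, for the device, check "That the device is provided only to eligible subjects". On oversight it says: "The Data Safety and Monitoring Board will comprise, at a minimum, the Clinical Director". Section 10.6 leaves it to the Clinical Director and/or that board to decide whether a deviation is taken into account in the analysis.

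**The concern.** Two things are at stake.

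**Safety.** Screening under 4.3 is an online survey, with hardcopy or verbal answers also accepted, and the protocol describes no clinical examination. The written criteria are thus the main barrier between an unsuitable candidate and the device. A clause that lets any of them be set aside by one role, with no stated grounds, weakens that barrier.

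**The endpoint.** The primary measure in 9.5 divides by the woman's baseline leak average. The lower leak limit keeps that divisor away from zero. If the limit can be waived, the measure can become very coarse or undefined, and the plan has no rule for that case.

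Because 9.5 is silent on waived women, their handling could be settled after the data are seen.

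**Working it through.** No stated figure is in dispute, so the main check is to set the sections side by side.

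**1. Does 4.1 agree with the rest of the protocol?**

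| Matter | Under 4.1 | Elsewhere |
|---|---|---|
| Baseline count below 1 or above 5 per day | Waivable, because the limits are in 4.2 | 5.4: the woman is disqualified and no device goes out; no waiver is mentioned |
| Unable to consent | Waivable, because it is in 4.2 | 11.2: not allowed to participate; no waiver is mentioned |
| Device release | Possible for a waived woman | 10.5: only eligible women receive it |

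The first two rows conflict as written. The third depends on reading. If a waived woman is still ineligible, 10.5 forbids sending her the device. If the waiver makes her eligible, the 10.5 check no longer constrains anything, because the person checking can redefine what is checked.

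**2. Is there an independent check?**
- Grants the waiver: the Clinical Director (4.1).
- Verifies eligibility and device release: the Clinical Director (10.5).
- Reviews compliance and adverse events: a board that includes the Clinical Director (10.5).
- Decides whether a deviation affects the analysis: the Clinical Director and/or that board (10.6). The "and/or" allows the role to decide alone.

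No step requires agreement from someone other than the person who granted the waiver. The plan also does not say whether an approved waiver is logged as a deviation at all.

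**3. How much can it matter?** Inputs: 20 women per group (5.2, 9.1); first and last five log entries (9.5).
- Responder rate: 1/20 = 5 points per woman, so 2 women carry 10 points and 3 carry 15. The number of waivers is not given; 1 to 3 is only an assumed range.
- Percent reduction: let b and f be total leaks in the first and last five entries. The measure is 100 × (b/5 − f/5)/(b/5) = 100 × (b − f)/b, so one leak more or less at the end moves it by 100/b points.
  - b = 25 (5 per day): 100/25 = 4 points.
  - b = 5 (1 per day, the lower limit): 100/5 = 20 points.
  - b = 2 (0.4 per day): 100/2 = 50 points.
  - b = 1 (0.2 per day): 100/1 = 100 points.
  - b = 0: undefined.

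The 5.4 limit is judged on 7 days and the endpoint on five entries, so the limit protects the divisor only approximately.

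**4. Would deleting the waiver keep low-leak women out?** Not by itself. The footnote to the leak exclusion in 4.2 excludes, on the baseline week, only women averaging fewer than 1 urge episode per day, and it counts episodes whether or not urine is lost. A woman with 0.2 leaks and 0.8 dry urge episodes per day has 0.2 + 0.8 = 1.0 and passes the footnote without any waiver. The primary measure in 9.5, however, counts leaks.

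**The case against.** The plan does contain safeguards. Approval is needed in advance and must be documented. Candidates receive the warnings and precautions at consent (7.2), and the IRB reviews the protocol (11.1). The board has at least two other members (10.5). Personnel doing the post-treatment analysis are blinded (9.3), and people outside the original analysis audit the data and calculations (10.6). The study is descriptive, and 9.5 disclaims rigorous comparison between groups. The protocol does not group any exclusions as electrical-safety items or give reasons for them. All of this stands, but none of it limits which criteria can be waived or requires a second approval.

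Three stronger readings are tempting and are not supported.

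- **That the waiver lets the Clinical Director choose a woman's group.** Section 9.2 says "Assignments are made alternating between Group 1 and 2 until enrollment is complete", so whoever knows the last shipment knows the next group. But the waiver precedes enrolment, while assignment is made at shipment, after the baseline week, verification and the deposit step. A waiver at screening leaves the group dependent on later shipping order. Foresight would be certain only if enrolment were completed at verification, and the documents do not fix that moment.
- **That the Clinical Director is unblinded and employed by the sponsor.** Section 5.7 says "Study staff will not be blinded to the treatment group", and 10.5 says the sponsor identifies the person. Both inferences are plausible; neither is stated.
- **That waived low-leak women would distort the result by a known amount or in a known direction.** One can construct a woman going from 0.2 to 1.0 leaks per day: (0.2 − 1.0)/0.2 = −400%, or −400/20 = −20 points on a mean of 20. That case is invented, it runs against the sponsor, and step 4 shows that it needs no waiver under the footnote. An equally hypothetical model points the other way. With Poisson leaks, no treatment effect, five entries at each end and at least one baseline leak, the chance of a ≥50% reduction is about 53% at 0.2 leaks per day against 19% at 1.0. No consistent bias follows.

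**Conclusion.** The point holds as a defect of governance and internal consistency. Section 4.1 gives one role an unrestricted power to waive, conflicts with 5.4 and 11.2, and either conflicts with the eligibility check in 10.5 or empties it. No independent approval or analysis rule offsets this.

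The size cannot be stated as an expected effect, because the number and kind of waivers are unknown. What can be said is that each woman carries 5 points of a 20-woman responder rate, which is true of any woman in the group. Below 1 leak per day, a single leak in the final entries moves that woman's percent reduction by more than 20 points, and with no baseline leaks the measure does not exist. The first figure assumes 20 analysed women per group; the second assumes five complete entries at each end.

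The conclusion does not rest on foreseeable assignment or on the Clinical Director's blinding or employer. It also takes no view on whether any particular exclusion is clinically needed. The sponsor wrote these criteria, and the question is only whether they bind.

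**What to change.** 1. In 4.1, delete the waiver for the 4.2 exclusions and the 5.4 baseline limits, so that 4.1 agrees with 5.4, 10.5 and 11.2. The self-reported minimum in 4.1 repeats the 4.2 leak limit and should follow it. If a waiver is kept for other inclusion items, require a second approver outside study management and list every waiver in the report.
2. Record any ineligible woman treated in error as a protocol deviation. Keep her in the main analysis if she otherwise qualifies for it (9.5 uses adherent women), and report a sensitivity analysis without her. Put this in 9.5 before data are seen, so that it does not depend on a later decision under 10.6.
3. Reconcile the 4.2 footnote with the leak-based limit and state which count 5.4 applies. If women with very few or no baseline leaks can still enter, 9.5 needs a rule for their percent reduction.

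None of the sponsor's exclusions is altered by steps 1 and 2. The cost is protocol wording, one extra descriptive analysis and perhaps a few lost candidates, in a study that recruits across the US (4.3, 4.4).
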